#### Change from Baseline

Change from baseline (CFB) will be calculated as (post-baseline – baseline).

#### **Discontinuation of study**

A subject will be considered discontinued from the study when a Study Exit CRF page is completed indicating primary reason for discontinuation.

#### **Protocol deviation**

Potential planned or unplanned protocol deviations noted during clinical monitoring will be documented by category (i.e., inclusion criteria, exclusion criteria, study drug, safety assessment, efficacy assessment, visit window, informed consent, prohibited medication, and other) and by whether or not the deviation excludes

PRS 005 T 17 F

the subject from the per protocol analysis set. All deviations will be reviewed, categorized, and finalized prior to database lock.

#### **Relationship to study treatment**

AEs related to study treatment will be defined as those entered as Related or Not Related. If relationship is missing, then it will be considered as related to study treatment.

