## 8.1.2 **Causality Categorization**

The investigator will assess causal relationship between the investigational product and each AE (i.e., their relationship to study drug), and answer "yes" or "no" to the question, "*Do you consider that there is a reasonable possibility that the event may have been caused by the investigational product*?"

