#### 12.6.1 Adverse Events

AEs reported from screening through EOS will be coded according to MedDRA® (Medical Dictionary for Regulatory Activities) version 20.0 or greater. Each reported AE will be mapped to a Preferred Term (PT) and a System Organ Class (SOC).

A treatment-emergent AE (TEAE) will be defined as an AE that began or worsened after the first dose of IP and no later than 30 days after the last dose of IP. AEs with insufficient date or time information to determine whether or not they were treatment-emergent will be considered treatment-emergent.

All TEAEs will be listed. In addition, separate listings will be done for non-treatment-emergent AEs and serious AEs (SAEs), treatment-emergent SAEs, and TEAEs that resulted in death, IP discontinuation, IP interruption, or dose reduction. Listings will include reported term, PT, and SOC; start and stop date; whether or not the AE was serious; severity; whether or not the AE was related to IP; action taken; and outcome.

Incidence and number of TEAEs will be summarized by SOC and PTs within SOCs. Summaries will include assessments of severity and relationship to IP. Missing severity will be considered severe and missing relationship will be considered related. Only the most related TEAE per subject for a given PT will be counted in summaries by relationship; similarly, only the most severe TEAE will be counted in summaries by severity. Separate summaries will be done for TEAEs related to IP and TEAEs resulting in IP discontinuation or interruption, or dose reduction. Summaries will be done separately for (a) all TEAEs and (b) treatment-emergent SAEs only.

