# Appendix 3 Tables, Figures, Listings, and Supportive SAS Output Appendices

List of Post-Text Tables, Figures :			
Output	Title	Analysis Set	
Table 14.1.1	Subject Disposition	Randomized	
Table 14.1.2.1	Baseline Characteristics	Safety	
Table 14.1.3.X	Medical History by System Organ Class and Preferred Term	Safety	
Table 14.1.4.X	Prior Medications by WHO Drug Dictionary Preferred Term	Safety	
Table 14.1.5.X	Concomitant Medications by WHO Drug Dictionary Preferred Term	Safety	
Table 14.2.1.1.1.1	Observed Values and Changes From Baseline in HAMD17 Total Score	mITT	
Table 14.2.1.1.2.1	Observed Values and Changes From Baseline in HAMD17 Bech Subscale (HAMD6)	mITT	
Table 14.2.1.1.3.1	Observed Values and Changes From Baseline in HAMD17 Anxiety/Somatization Subscale	mITT	
Table 14.2.1.1.4.1	Observed Values and Changes From Baseline in HAMD17 Gibbons Subscale	mITT	
Table 14.2.1.2.1.1	HAMD17 Total Score Response	mITT	
Table 14.2.1.3.1.1	HAMD17 Total Score Remission	mITT	
Table 14.2.2.1.1.1	Observed Values and Changes From Baseline in EPDS Total Score	mITT	
Table 14.2.2.1.2.1	Observed Values and Changes From Baseline in EPDS Anxiety Subscale		
Table 14.2.3.1.1.1	Observed Values and Changes From Baseline in STAI6 Total Score	mITT	
Table 14.2.4.1.1	CGI-Improvement	mITT	
Table 14.3.1.X	Treatment Exposure (IV/Infusion)	Safety	
Table 14.3.1.3	Treatment Exposures	Safety	
Table 14.3.2.1	Summary of Treatment-Emergent Adverse Events (TEAEs)	Safety	
Table 14.3.2.2.1	Incidence and Number of Treatment-Emergent Adverse Events	Safety	
Table 14.3.2.2.2	Incidence and Number of Treatment-Emergent Adverse Events Related to Investigational Product	Safety	
Table 14.3.2.2.3	Incidence and Number of Treatment-Emergent Adverse Events Resulting in Investigational Product Discontinuation	Safety	
Table 14.3.2.2.4	Incidence and Number of Treatment-Emergent Adverse Events Resulting in Investigational Product Dose Reduction or Interruption	Safety	
Table 14.3.2.2.5	Incidence of Treatment-Emergent Adverse Event Preferred Terms in Order of Descending Incidence Among All Subjects	Safety	
Table 14.3.2.3.1	Incidence and Number of Treatment-Emergent Serious Adverse Events	Safety	

PRS 005 T 17 F

Page 32 of 35

Table 14.3.2.3.2	Incidence and Number of Treatment-Emergent Serious Adverse Events Related to Investigational Product	Safety
Table 14.3.2.3.3	Incidence and Number of Treatment-Emergent Serious Adverse Events Resulting in Investigational Product Discontinuation	Safety

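### Read literally, the SAP's definition of a treatment-related AE leaves no AE unrelated, so the related-TEAE tables would repeat the all-TEAE tables

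*SAP*

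**What the plan says.** SAP 8.2 (Other Definitions, entry on relationship to study treatment) consists of two sentences. The first is the definition: "AEs related to study treatment will be defined as those entered as Related or Not Related". The second covers blanks: "If relationship is missing, then it will be considered as related to study treatment".

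SAP 12.6.1 uses the term without redefining it. It repeats the rule for blanks ("Missing severity will be considered severe and missing relationship will be considered related") and plans outputs that depend on the term: "Separate summaries will be done for TEAEs related to IP and TEAEs resulting in IP discontinuation or interruption, or dose reduction". Appendix 3 gives these outputs numbers: Table 14.3.2.2.2, "Incidence and Number of Treatment-Emergent Adverse Events Related to Investigational Product", and Table 14.3.2.3.2, "Incidence and Number of Treatment-Emergent Serious Adverse Events Related to Investigational Product".

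On the protocol side, 8.1.2 says: "The investigator will assess causal relationship between the investigational product and each AE". The answer there is yes or no, and 8.1.3 lists the same binary variable. Protocol 9.5.7 plans TEAE incidence by relatedness within each cohort. Protocol 9.4 sets a missing relationship to related, but only for AEs that occur after IP has been given.

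**The concern.** A definition of related AEs should separate two groups. This one names both entered categories as belonging to the related group, and the rule for blanks then adds the only remaining possibility. Because 12.6.1 offers no competing definition, 8.2 is the text a programmer would turn to when deriving the relatedness flag.

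What is at stake is the aggregate view of causality by treatment arm and cohort. The study's stated purpose is to find a dose and exposure level that is safe and well tolerated. A related-TEAE table that merely copies the all-TEAE table gives no information on which events investigators attributed to the study drug, while its title says that it does.

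**Working it through.** No sample size, power or error-rate figure is involved, and the plan states no number to reproduce. The check is to list every value the relationship field can hold and classify each one under the two rules.

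**Inputs.** The entered values are Related and Not Related (SAP 8.2), corresponding to yes and no (protocol 8.1.2 and 8.1.3). The field can also be missing (SAP 8.2 and 12.6.1; protocol 9.4).

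**Rules.** Literal 8.2: related if the entry is Related, or Not Related, or missing. Corrected: related if the entry is Related, or is missing for an AE after IP administration.

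| Field value | Literal SAP 8.2 | Corrected rule |
|---|---|---|
| Related (yes) | related | related |
| Not Related (no) | related | not related |
| Missing, AE after IP administration | related | related |

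Under the literal rule 3 of 3 values are related, so 100% of AEs are related whatever the investigators answered. Under the corrected rule 2 of 3 are, and every AE answered no is separated out.

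**Consequence for the outputs.** If all TEAEs are related, the set behind Table 14.3.2.2.2 is the set behind Table 14.3.2.2.1, and the set behind 14.3.2.3.2 is the set behind 14.3.2.3.1. Each pair would be identical, cell for cell. A summary by relationship built on the same flag would have an empty not-related category in both arms.

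**Is the literal rule the intended one?** Four places say it is not:

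- SAP 12.6.1 counts, for each subject and preferred term, only the TEAE with the strongest relationship. That rule has no function if all TEAEs are equally related.
- The listings in 12.6.1 carry a column showing for each AE whether it was related. That column presupposes both answers.
- The rule for blanks assigns missing to the related side, which is a choice only if there is another side.
- SAP 4.0 says that substantial departures from the protocol's statistical text are identified in 4.1. Section 4.1 lists changes for the C-SSRS, the physical examination and the Per Protocol Set, and none for relatedness.

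**The rule for blanks.** Protocol 9.4 limits it to AEs after IP administration. SAP 12.6.1 states it among the TEAE summaries, where that limit largely holds already. SAP 8.2 states it without a limit, although AEs are collected from consent onward. The practical effect is small, since the summaries concern TEAEs, but the definition should carry the limit.

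**The case against.** The best case on the other side is that no competent programmer would be misled. The sentence evidently meant to say that relationship is recorded in two categories, and the surrounding text in 12.6.1 makes that plain. Two pairs of identical tables would also be conspicuous on review. Most of this stands. It is why the point is a wording correction and not a dispute about method.

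It does not remove the point, for three reasons. A definition in a SAP exists so that intent need not be guessed. The AE tables after Cohorts 1-3 are to be produced outside the group that wrote the SAP (SAP 10.2), so more than one team may work from this text. And detection is likely but not assured: pre-lock review of outputs is conditional on the contract (SAP 11.2), and quality control is deferred to a separate plan (SAP 13.0).

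A reader might also infer more than the documents support:

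- *That the investigators' causality judgement would be lost.* It would not. The yes/no answer is collected for each AE, and the listings show relatedness per event. Only the aggregated outputs are at risk, and they can be rerun.
- *That an output of the primary objective is compromised.* Neither document ranks the safety, efficacy and pharmacokinetic objectives; the word primary is attached to the HAMD17 endpoint. The tables of all TEAEs, severity, all serious TEAEs and discontinuations do not use this definition.
- *That every AE will be reported as related.* That follows only if the sentence is programmed literally, against the evident sense of 12.6.1.

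**Conclusion.** The definition in SAP 8.2 is wrong as written. Taken literally it classes 100% of AEs as related, makes two planned tables (14.3.2.2.2 and 14.3.2.3.2) duplicates of two others (14.3.2.2.1 and 14.3.2.3.1), and empties the summaries by relationship of content. It contradicts SAP 12.6.1 and the protocol's binary causality item.

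The conclusion rests on two things: that the field has only the two entered values plus missing, which both documents support, and that the harm arises only under literal programming. No efficacy result changes, and listings of the recorded value are unaffected. The documents do not show how many AEs in this trial would be misclassified; that number is the count of TEAEs answered no. Severity is low, but the sentence governs planned safety tables and should be corrected.

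**What to change.** Replace the two sentences in SAP 8.2 with: *AEs entered as Related (causality answer yes) are related. AEs entered as Not Related (answer no) are not related. If relationship is missing for an AE occurring after IP administration, it is treated as related.* This ties the SAP's labels to the protocol's yes/no item and restores the limit in protocol 9.4. SAP 12.6.1 and Appendix 3 need no change.

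The cost is a short SAP amendment, which SAP 3.0 permits up to unblinding, with no change to data collection. If a relatedness flag has already been programmed, or tables for Cohorts 1-3 produced, check that events answered no are absent from the related tables, and rerun those tables if they are not.

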#### Study day

Study day is defined relative to the date of the first dose of study drug. For assessments that occur after this visit date, study day is calculated as (assessment date – study drug first dose date + 1). For assessments that occur prior to study drug first dose date, study day will be calculated as (assessment date – study drug first dose date); there is no Study Day 0.

#### Study time

Study time (in minutes) is defined relative to the time of the first dose of study drug (0 hour on the morning of Day 1).

#### 8.3 Imputation

While every attempt must be made by the investigator to provide complete data, there are cases in which this may not always be possible (e.g., incomplete subject recall of start and stop dates). Unrecorded values will be treated as missing in summaries and analyses unless otherwise noted.

### 8.4 Analysis Time Point/Visit Windows

For data summarized on a per time point or per visit basis, the windows used for analyses are defined below unless stated otherwise.

Protocol Visit	Window Description (Target Day/Time Point)	Protocol Window (with respect to Visit Day as defined in the protocol)	Analysis Window (with respect to Study Day and Study Time in minutes as defined in this SAP)
Screening	Screening	Day -14 to -1	Study Day < -1
Day 0	Day 0 (Admission)	Day 0	Study Day = -1
Day +1	Day 1 (Pre-Infusion)	N/A	Study Day = 1 and Study Time < 0
Day +1	Day 1 (+4h)	N/A	0 <= Study Time < 360
Day +1	Day 1 (+8h)	N/A	360 <= Study Time < 600
Day +1	Day 1 (+12h)	N/A	600 <= Study Time < 900
Day +1	Day 1 (+18h)	N/A	900 <= Study Time < 1260
Day +2	Day 2 (+24h)	N/A	1260 <= Study Time < 1680
Day +2	Day 2 (+32h)	N/A	1680 <= Study Time < 2160
Day +2	Day 2 (+40h)	N/A	2160 min <= Study Time < 2640 min
Day +3	Day 3 (+48h)	N/A	2640 min <= Study Time < 3120 min
Day +3	Day 3 (+56h)	N/A	3120 min <= Study Time < 3480 min
Day +3	Day 3 (+60h)	N/A	3480 min <= Study Time < 3960 min
Day +4	Day 4 (+72h)	N/A	3960 min <= Study Time < 2 days after 72 hr timepoint

For the IV only cohorts (cohorts 1-5), the following analysis time points and visit windows will be used.

PRS 005 T 17 F

Strictly Confidential. © 2004-2015, PRA Health Sciences. All rights reserved.

Page 16 of 35

Protocol Visit	Window Description (Target Day/Time Point)	Protocol Window (with respect to Visit Day as defined in the protocol)	Analysis Window (with respect to Study Day and Study Time in minutes as defined in this SAP)
Day 11	Day 11	Day 8 to 14	5 <= Study Day < 23
Day 34	Day 34	Day 29 to Day 39	23 < Study Day < 45

For the IV to oral cohort (cohort 6), the following analysis time points and visit windows will be used.

Protocol Visit	Window Description (Target Day/Time Point)	Protocol Window (with respect to Visit Day as defined in the protocol)	Analysis Window (with respect to Study Day and Study Time in minutes as defined in this SAP)
Screening	Screening	Day -14 to -1	Study Day < -1
Day 0	Day 0 (Admission)	Day 0	Study Day = -1
Day +1	Day 1 (Pre- Infusion)	N/A	Study Day = 1 and Study Time < 0
Day +1	Day 1 (Post- Infusion)	N/A	Study Day = 1 and Study Time >= 0
Day 2	Day 2 (Discharge)	N/A	Study Day = 2
Day 4	Day 4 (HAMD Call)	Day 3 to 5	3 <= Study Day <= 5 for HAMD only
Day 8	Day 8	Day 6 to 10	6 <= Study Day <= 9 for HAMD, 3 <= Study Day <= 11 otherwise
Day 11	Day 11 (HAMD Call)	Day 10 to 12	10 <= Study Day <= 12 for HAMD only
Day 15	Day 15	Day 12 to 18	13 <= Study Day <=18 for HAMD, 12 <= Study Day <= 18 otherwise
Day 22	Day 22	Day 19 to 25	19 <= Study Day <= 25
Day 29	Day 29	Day 26 to 32	26 <= Study Day <= 32
Day 36	Day 36	Day 33 to 39	33 <= Study Day <= 46
Day 57	Day 57	Day 54 to 60	47 <= Study Day <= 64
Day 71	Day 71	Day 68 to 74	65 <= Study Day <= 77

The analysis windows are aligned with, but wider than, those specified by the schedule of visits and procedures in the protocol in order to include in analyses of all study data (including unscheduled visit data) that fall outside of protocol visit windows. If multiple data points are observed within a single analysis window, the latest observation will be used for analysis.

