### 7.3.2 **During Infusion (Days +1 to +4)**

- Start bolus/infusion in the morning of Day +1 (0h) after baseline assessments are completed
- CTNI to conduct interviews for HAMD17 (+12h, +24h, +48h, +60h, +72h)
- Conduct interviews for CGI-I (+12h, +24h, +48h, +60h, +72h)
- EPDS (+60h)
- STAI6 (+12h, +24h, +48h, +60h, +72h)
- Collect AEs
- Collect ECG (+12h, +24h, +48h, +72h)
- Collect VS (BP, pulse, respiratory rate, pulse oximetry, temperature): (+4, +8h, +12, +18h, +24h, +32h, +40h, +48h, +56h, +60h, +72h)
- Collect SSS (+8h, +32h, +56h, +72h)
- Collect pharmacokinetic samples (+12h, +24h, +48h, +72h)
- Record concomitant medications
- Lower the infusion rate to half what was prescribed for the cohort (for example, lower the infusion rate from 4 mg/h to 2 mg/h) (+48h)
- Collect safety laboratory tests (+48h)
- Collect neurosteroid level (+48h)
- End infusion (+60h)
- Collect urine sample for urinalysis, drug screen and urine pregnancy test (+72h)
- Conduct CSSRS interview (+12h, +36h, +60h, +72h)
- Perform a physical examination (+72h)

- Stop monitoring of pulse oximetry and Q15 min health checks (+72h)
- Discharge subject (+72h)

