#### Specific timepoints for assessments on days +1, +2, +3 and +4: - Cohorts 1-5

PK samples: +12h, +24h, +48h, +72h HAMD17: before start of infusion, +12h, +24h, +48h, +60h, +72h all done by CTNI CGI-I: +12h, +24h, +48h, +60h, +72h CGI-S: before start of infusion EPDS: before start of infusion, +60h STAI6: before start of infusion, +12h, +24h, +48h, +60h, +72h ECG: +12h, +24h, +48h, +72h Vital Signs: (BP/P/pO2/RR/Temp): before start of infusion, +4, +8h, +12, +18h, +24h, +32h, +40h, +48h, +56h, +60h, +72h SSS: before start of infusion, +8h, +32h, +56h, +72h CSSRS: before start of infusion, +12h, +36h, +60, +72h Safety laboratory tests and neurosteroid level: +48h Urinalysis drug and pregnancy test: +72h Physical examination: +72h AEs and concomitant medications are collected throughout the inpatient stay.

Q15min health checks are done from the time of admission to the time of discharge. Pulse oximetry (pO2) must be monitored throughout the infusion, including during the night when the subject is sleeping. The subject should be awakened if pulse oximetry falls < 91%.

The following priority order will be in effect when more than 1 assessment is required at a particular time point: 1) HAMD17 2) CGI-I/CGI-S 3) EPDS 4) STAI6 5) SSS 6) CSSRS 7) vital signs 8) ECG 9) safety labs and neurosteroid level 10) PK sample 11) neurosteroid level 12) urinalysis drug screen and pregnancy test 13) physical examination

Day 11 and Day 34 visits have visit windows of  $\pm$  3 and  $\pm$  5 days, respectively

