### 8.2 Other Definitions

#### +72h

72 hours after start of infusion (0hr) based on visit window. If a subject is discontinued from the study during the inpatient treatment phase (Day 1 through Day 4), all assessments scheduled at +72h will be collected at the time of study exit, but the assessments will be allocated to analysis visits based on visit windows detailed in Section 8.4.

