# 12.0 Statistical Methods

Data analyses will primarily be descriptive. The purpose of this study is to identify a ganaxolone dose and exposure level that is safe and well tolerated. Efficacy data will be collected but will be considered hypothesis-generating; i.e., there are no *a priori* hypotheses on which the study was powered. Results from exploratory statistical analyses may be presented but only to aid in interpretation.

Unless otherwise indicated, continuous variables will be summarized with the following descriptive statistics: n (number of observations), (arithmetic) mean, standard deviation (SD), first and third quartiles (Q1 and Q3), minimum (min) value, median, and maximum (max) value. The minimum and maximum values will be displayed to the same level of precision as the raw data, the median and mean to a further decimal place and the SD to two additional decimal places – up to 4 decimal places total.

Categorical data will be summarized with frequencies and percentages. Percentages by categories will be based on the number of subjects exposed within a treatment. Percentages will be rounded to one decimal place.

All analyses will use SAS version 9.4 or higher. Tables will present data summarized by treatment group within cohort. For each summary table, corresponding supportive listing(s) will be provided.

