### 12.6.4.5 Columbia-Suicide Severity Rating Scale (C-SSRS)

For the 5 suicidal ideation questions ("Wish to be dead," "Non-specific active suicidal thoughts," "Active suicidal ideation with any methods (not plan) without intent to act," "Active suicidal ideation with some intent to act, without specific plan," "Active suicidal ideation with specific plan and intent") and the 5 suicidal behavior questions ("Preparatory acts or behavior," "Aborted attempt," "Interrupted attempt," "Suicide attempt," "Suicide behavior") of the C-SSRS, the number of subjects who answered "yes" will be tabulated for each applicable study time point. Other data collected on the C-SSRS (e.g., ideation intensity measures) will be provided in data listings only.

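### SAP 8.4 has no row for the +36h C-SSRS in Cohorts 1-5, and it files a compliant Day 10 Visit 4 HAMD17 in Cohort 6 under Day 11

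*SAP*

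**What the plan says.** **C-SSRS, Cohorts 1-5.** Protocol 7.3.2 lists the interview at +12h, +36h, +60h and +72h. The time-point list under Protocol Table 1 agrees ("CSSRS: before start of infusion, +12h, +36h, +60, +72h"), and SAP Table 1 repeats it. SAP 12.6.4.5 says that yes answers "will be tabulated for each applicable study time point" and sets no window of its own, so the general windows of SAP 8.4 apply. Those have rows at +4, +8, +12, +18, +24, +32, +40, +48, +56, +60 and +72h. The +40h row is "2160 min <= Study Time < 2640 min", and the +32h row covers 1680 to under 2160 minutes.

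**HAMD17, Cohort 6.** The Protocol Table 2 footnote gives Visit 4 (Day 8) two days either side and Visit 5 (Day 11) one day either side. The protocol-window column of SAP 8.4 also shows Days 6 to 10 for Visit 4. The analysis window for Day 8 is "6 <= Study Day <= 9 for HAMD, 3 <= Study Day <= 11 otherwise", and for Day 11 it is "10 <= Study Day <= 12 for HAMD only". When several values fall in one window, SAP 8.4 keeps only the last. It describes its windows as broader than the protocol's, so that all study data can be included.

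**The concern.** In both places a subject who follows the schedule is put in the wrong row.

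The +36h C-SSRS is the only one scheduled between +12h and +60h of the infusion. Under the written windows, a few minutes either way decide whether it appears as +32h or +40h. No row of the suicidality table shows the +36h result.

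In Cohort 6, the HAMD17 from a Visit 4 held on its last allowed day is reported under another visit, while the EPDS, STAI6 and CGI-I from that same visit are reported at Day 8. If the Visit 5 call follows, the rule that keeps the last value discards the Visit 4 rating. This touches the by-visit HAMD17 change, response and remission, which are secondary endpoints, and one visit level of the MMRM. For HAMD17 the Day 8 window is narrower than the protocol's, contrary to the SAP's own description.

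**Working it through.** **C-SSRS.** The inputs are the four scheduled times, study time counted in minutes from first dose (SAP 8.2), and the SAP 8.4 rows.

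The SAP's cuts are midpoints of neighbouring labels. For the cut in question, (32 + 40)/2 = 36h, and 36 x 60 = 2160 min, which reproduces the stated figure. The other nine cuts follow the same rule; for example, (60 + 72)/2 = 66h = 3960 min. The grid leaves out 36h, so 36h became a boundary.

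| Scheduled | Minutes | SAP 8.4 row | Minutes to nearest cut |
|---|---|---|---|
| +12h | 12 x 60 = 720 | +12h, 600 to <900 | 720 - 600 = 120 |
| +36h | 36 x 60 = 2160 | none; it is the cut | 0 |
| +60h | 60 x 60 = 3600 | +60h, 3480 to <3960 | 3600 - 3480 = 120 |
| +72h | 72 x 60 = 4320 | +72h, from 3960 | 4320 - 3960 = 360 |

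An interview at 35h50 (2150 min) is tabulated as +32h, and one at 36h10 (2170 min) as +40h.

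Can the result be recovered from the table? The two rows together span 1680/60 = 28h to 2640/60 = 44h. SAP 12.0 says "Percentages by categories will be based on the number of subjects exposed within a treatment", so both rows share a denominator, and counts and percentages can be added. For scheduled interviews held between 28h and 44h the sum is the +36h count. It need not be exact otherwise, because for early exits "the assessments will be allocated to analysis visits based on visit windows detailed in Section 8.4", and such an interview can fall in either row.

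**HAMD17, Cohort 6.** First dose is on Study Day 1, so Study Day 10 is protocol Day 10.

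- Visit 4: 8 - 2 = 6 to 8 + 2 = 10.
- Visit 5: 11 - 1 = 10 to 11 + 1 = 12.
- The two protocol windows share Day 10.
- The midpoint of the two targets is (8 + 11)/2 = 9.5, so the SAP gives Day 10 to Day 11.

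For a Visit 4 held on Day 10:

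- If no later HAMD17 falls in Days 10-12, the rating is analysed as Day 11. Day 8 is blank unless an unscheduled rating falls in Days 6-9.
- If a later HAMD17 does fall in Days 10-12, such as the Visit 5 call on Day 11 or 12, only that one is kept. The Visit 4 rating then leaves the by-visit summaries and the MMRM.
- EPDS, STAI6 and CGI-I use Days 3-11 and are analysed as Day 8 either way.

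Mapping every protocol-compliant HAMD17 day for the Day 4 to Day 71 visits onto the SAP windows gives one mismatch: Visit 4 on Day 10.

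**Primary windows.** +60h is 3600 min, inside 3480 to <3960. Day 29 has protocol limits 29 - 3 = 26 and 29 + 3 = 32, the same as its analysis window.

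**The case against.** On the C-SSRS, this is largely a matter of labels. The table counts yes answers without a test, every interview is in Listing 16.2.13.X, and the two rows can be added. All of that stands. A reader might infer that suicidality data are lost, or that a subject's positive answer could go unnoticed. The documents do not support either reading: the answers are listed, and Protocol 4.4.1 has a subject with suicidal ideation or behaviour evaluated at once, without reference to any summary table. What remains is a table whose rows do not match the schedule.

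On Day 10, the overlap comes from the protocol. Any rule based on date alone must give Day 10 to one visit, and the SAP chose the nearer target. Extending Day 8 to Day 10 by date would misfile compliant Visit 5 calls instead. That also stands, and it is why date alone cannot settle Day 10.

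A reader might note that Day 10 is one of five allowed Visit 4 days and infer that a fifth of the ratings are displaced. The documents give no distribution of visit days, so no frequency can be stated.

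A reader might also take the SAP 8.4 entry of Days 12 to 18 for Day 15 as a third misallocation. It does conflict with the two-day window in Protocol 7.6.5, the Protocol Table 2 footnote and the SAP Table 2 footnote, which gives Days 13-17. But both operative windows for that visit (13-18 for HAMD17, 12-18 otherwise) contain every compliant day. It is a clerical note only.

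**Conclusion.** Both points hold, and both are minor.

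1. The +36h C-SSRS has no row, and interviews done on time are split between +32h and +40h. The error is confined to the by-time-point suicidality table. That the two rows add up to the +36h count assumes scheduled interviews held between 28h and 44h; the documents state no tolerance for inpatient times.
2. A compliant Day 10 Visit 4 HAMD17 is missing from Day 8. It leaves the by-visit summaries and the MMRM only when a later HAMD17 falls in Days 10-12. The frequency is unknown.

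It would be wrong to conclude that the primary endpoint is misallocated: the +60h and Day 29 windows hold every value they should. A displaced earlier rating could reach the Day 29 model estimate only indirectly, through the within-subject covariance of the MMRM.

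**What to change.** Amend SAP 8.4 before unblinding, as SAP 3.0 allows.

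1. For the C-SSRS only, in Cohorts 1-5, replace the +32h and +40h rows with one +36h row, 1680 <= study time < 2640 min. Leave the other rows unchanged. Count a yes if any interview in the window is yes. Without that rule, keeping only the last value could let an early-exit or unscheduled interview overwrite a scheduled yes in the merged row.
2. For a HAMD17 on Study Day 10 only, assign by CRF visit label: Visit 4 to Day 8, the Visit 5 call to Day 11. Leave all other windows unchanged, including Day 29.

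As a clerical correction, reconcile the Day 15 protocol-window entry with the two-day window stated elsewhere.

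The cost is minor reprogramming and reliance on the visit label for one study day. No new data are collected.
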